7.1.3. Packaging and Labeling

Tablets

The label(s) for apremilast will include drug name, dosage form and strength (where applicable), amount of apremilast per container, lot number, expiry date (where applicable), dosing instructions, storage conditions. All apremilast will be supplied by Amgen in HDPE bottles with child-resistant caps.

7.1.4. Product Accountability and Disposal

The Investigator, or designee, is responsible for taking an inventory of each shipment of Otezla received, and comparing it with the accompanying Otezla shipping order/packing list.

The Investigator, or designee, will verify the accuracy of the information on the form, sign and date it, retain a copy in the study file, and return a copy to Amgen.

Investigational product will be stored per the storage conditions identified on drug label. At the study site, all Otezla will be stored in a locked, safe area to prevent unauthorized access.

Amgen will instruct the Investigator on the return, disposal and/or destruction Otezla if applicable.

7.1.5. Investigational Product Compliance

Study personnel will review the instructions printed on the package with the study subjects prior to dispensing Otezla. The subjects will be instructed to return the Otezla containers, including any unused medication, to the study site at each visit for tablet counts and reconciliation. Subjects will be asked whether they have taken their Otezla as instructed at each study visit and will be required to complete a medication log at home that will be returned at study visits 3-6. Any problems with compliance will be reviewed with the subject.

7.1.6. Rescue Therapy

The initiation of non-study drug therapy to treat worsening of psoriasis, or flare of previously inactive skin disease, is strongly discouraged throughout the treatment period. However, should rescue therapy be required for the safety and well-being of the subject, such use will be permitted. The subject may remain on study drug, unless the rescue therapy is any therapy that may jeopardize the subject's safety if study drug is continued, in the investigator's and/or Sponsor's opinion. Because the study is not a randomized trial, any subjects that are required to be placed on rescue therapy, but continue in the study will have any data after rescue treated as missing values. Missing values will be imputed from the average of all subjects completed for those data points. Alternatively if rescue therapy is required for > 50% of the patients, then these individuals would be analyzed as a separate cohort of patients and will not be analyzed in the grouped data.

8. CONCOMITANT MEDICATIONS AND PROCEDURES

8.1. Permitted Concomitant Medications and Procedures

Subjects may take any medication that is not restricted by the protocol and would not be expected to interfere with the conduct of the study or affect assessments. Chronic medication should be dosed on a stable regimen.

All medications (prescription and non-prescription), treatments and therapies taken by the subject from screening throughout their entire participation in the study, including those initiated prior to the start of the study, must be recorded on the subject's source document and on the appropriate page of the eCRF. The dose, unit, frequency, route, indication, the date the medication was started and the date the medication was stopped (if not ongoing) must be recorded. The recording of any permitted topical medications taken for psoriasis should also include the area of the body to which they are applied.

The following topical therapies will be permitted:

- Low-potency or weak corticosteroids (e.g., Class 6 or 7 in US, such as hydrocortisone, desonide, alclometasone dipropionate) will be allowed as background therapy and restricted to treatment of the face, axillae, and groin in accordance with the manufacturers' suggested usage during the course of the study (this restricted usage should be documented).
- Subjects with scalp psoriasis will be permitted to use coal tar shampoo and/or salicylic acid scalp preparations on scalp lesions.
- An unmedicated skin moisturizer (e.g. Eucerin) will be also permitted for body lesions only.

8.2. Prohibited Concomitant Medications and Procedures

The following psoriasis medications cannot be administered for the duration of the study.

- Topical therapy
 - Topical therapy, unless otherwise specified (including, but not limited to, topical corticosteroids, retinoids or vitamin D analog preparations, tacrolimus, pimecrolimus, or anthralin/dithranol; or as specified as in Section 8.1).
- Systemic Therapy
 - Systemic therapy including but not limited to cyclosporine, corticosteroids, methotrexate, retinoids, mycophenolate, thioguanine, hydroxyurea, sirolimus, sulfasalazine, azathioprine, fumaric acid esters.

- Phototherapy
 - UVB or PUVA unless otherwise specified as in Section 8.1
- Biologic agents, including:
 - Adalimumab, etanercept, infliximab, or certolizumab pegol
 - Ustekinumab
 - IL-17-inhibitors, brodalumab, ixekizumab and secukinumab
- Use of any investigational drug or device
- Prolonged sun exposure or use of tanning booths or other ultraviolet light sources

8.3. Required Concomitant Medications and Procedures

Not applicable.

9. STATISTICAL ANALYSES

9.1. Overview

The objective of the statistical analysis will be to evaluate change in aberrant inflammatory profiles of activated blood monocytes (aberrant-monocyte endotype patients (AM-endotype). Subjects with moderate to severe plaque psoriasis will be treated with oral apremilast (Otezla) with standard dosing for 16 weeks. For each subject, we will identify a target biomarker of abnormally elevated monocytes, among intermediate, doublets, and platelet doubles. Each subject will thus have one identified monocyte biomarker for which relative percent change will be its basis for analysis in the primary outcome. If more than one category is abnormally elevated, then among abnormally elevated monocyte biomarkers we will first select doublets if elevated. If not, then we will select intermediate monocytes. For each of the selected abnormally elevated monocyte biomarkers, our focus will be on relative percent reduction. We will specifically assess change from baseline to 16 weeks by computing relative percent reduction for each subject being treated. Note for example that a change of 1.5% to 1.2% is $(1 - (1.2/1.5)) * 100\% = 20\%$ reduction. The median and other summary statistics of these percent change values will be computed. Wilcoxon's signed rank test will be used to evaluate the null hypothesis of the median percent change being 0. In other words, we will test whether or not there has been a reduction in abnormally elevated monocytes.

Secondarily, in an exploratory manner, we will longitudinally model these percent change values across time points (baseline, 4, 8, 12, and 16 weeks), to assess trajectory of percent change values. We will test for time effects, and consider post-hoc pairwise analyses of time points. Time will be considered as both a continuous covariate with slope parameter, as well as a categorical variable, which does not require linearity assumptions.

In analyses treating time as a continuous variable, actual measurements of time (as compared to fixed time points by week) will be used in the analyses.

Other outcomes such as PASI will be analyzed similarly. Note that we will also correlate change in our abnormally elevated monocyte markers at various time points with change in PASI, to explore possible mechanistic associations. For a two-sided Wilcoxon test with Type I error of 0.05, power is 0.80 if the effect size is 0.60 or greater (assuming an underlying normal distribution). For 20% median reduction, as long as standard deviation of percent change is not larger than 33%, we will have effect size of at least 0.60. These are plausible assumptions given our prior work on treatment related monocyte reductions [40].

Because the study is not a randomized trial, any subjects that are required to be placed on rescue therapy, but continue in the study will have any data after rescue treated as missing values and these missing values will be imputed from the average of all subjects completed. Alternatively if rescue therapy is required for > 50% of the patients, then these individuals would be analyzed as a separate cohort of patients and will not be analyzed in the grouped data.

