- Assess the median reduction of abnormal monocyte biomarker values in AM-endotype patients treated with oral apremilast (Otezla) under recommended dosing:
 - Day 1: 10 mg in morning
 - Day 2: 10 mg in morning and 10 mg in evening
 - Day 3: 10 mg in morning and 20 mg in evening
 - Day 4: 20 mg in morning and 20 mg in evening
 - Day 5: 20 mg in morning and 30 mg in evening
 - Day 6 - Day 112: 30 mg twice daily

Secondary Objectives

- Evaluate the median change in serum myeloperoxidase, resistin, IL-17, and Tissue Factor in the AM-endotype.
- Evaluate the median change in flow cytometric quantitation of additional monocyte and neutrophil markers, including CD18/CD11b and NETotic neutrophils.
- Evaluate change in monocyte transcriptome biomarkers by WGS.

Other Objective(s)

[figure not shown]
- Evaluate Health Related Quality of Life (HRQoL) (Dermatology Life Quality Index (DLQI) and (Work Productivity and Activity Impairment Questionnaire: Psoriasis (WPAI: PSO)) and changes in symptom severity of patients receiving apremilast 30 mg BID.
- Explore potential change in Framingham Risk profile of treated patients.

Study Design

This is an open label pilot study of the impact of treatment with standard dosing of APM for 16 weeks on AM-endotype psoriasis patients, identified by elevated (>150% of normal):

1. Intermediate (CD14⁺⁺CD16⁺) monocytes (i.e. monocytes in circulation), OR
2. Circulating monocyte doublets (i.e. adherent monocyte-monocyte pairs), OR
3. Circulating monocyte-platelet aggregates (i.e. monocytes adherent to platelets; MPA).

Study Design

Approximately 25 psoriasis patients with the AM-endotype will be followed during treatment over 16 weeks with 5 monthly individual blood draws will be enrolled. 10 untreated healthy controls will also be enrolled and will provide two blood draws (baseline and 16 weeks). These are needed to maintain quality control of the normal levels of the biomarkers being tested. All treated psoriasis subjects will receive apremilast through Week 16

Study Population

Adult subjects 18-65 years of age with moderate-to-severe plaque psoriasis.

Healthy controls

Healthy participants will be recruited from a pool of generally healthy research volunteers. Healthy volunteers will be selected to match age, sex, and race of psoriasis subjects as closely as possible.

Length of Study

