The study is designed as a 16 week study and consists of 6 distinct visits as described above. Screening will consist of a 1a and optional 1b visit. Visit 1b is optional. It exists so that the subject can pick up the Empatica E4 wrist device that cannot be given until their monocyte profile is known. Visits 3 and 5 will also be split into part a and b. Visit b will be optional. If the subject chooses to participate, visit b is when the subject returns the wrist device.

Study Treatments

Apremilast will be dispensed in dose titration cards at Visit 2. At Visit 3, apremilast tablets will be supplied in high density polyethylene (HDPE) bottles containing approximately 60 tablets each.

Overview of Efficacy Assessments

Primary Clinical Assessment

The primary clinical assessment will be Psoriasis Area and Severity Index (PASI) scores.

Additional Clinical Assessments

- Static Physician's Global Assessment (sPGA)
- Body Surface Area (BSA)
- Subject's Assessment of Pruritus VAS
- Subject's Assessment of Skin Discomfort/Pain VAS
- Subject Global Assessment of Psoriasis Disease Activity VAS
- Subject's Assessment of Joint Pain VAS
- Subject Global Assessment of Psoriatic Arthritis Disease Activity VAS
- Health Related Quality of Life (HRQoL) questionnaires:
 - Dermatology Life Quality Index (DLQI)
 - Work Productivity and Activity Impairment Questionnaire: Psoriasis (WPAI: PSO)

Overview of Safety Assessments

Safety Assessments

- Adverse events (AE)
- Physical examinations
- Vital signs
- Clinical laboratory tests
- Evaluation of psoriasis flare or rebound.

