4. TABLE OF EVENTS

	Screening Part 1	Screening Part 2	Baseline 2A	Baseline 2B	Apremilast Treatment					
Visit	1a	1b	2A	2B	3	3b	4	5	5b	6
Week	Up to 35 days		0	1	4	5	8	12	13	16
Informed Consent	X		-	-						
Inclusion/Exclusion Criteria	X									
Medical and Disease History	X		X							
Prior/Concurrent Medications/Therapies	X	X	X		X		X	X		X
Peripheral blood draw	X		X		X		X	X		X
Safety Assessments										
Pregnancy Test and Contraception Education for Females of Child-bearing Potential (FCBP)	X		X							
Vital Signs	X		X		X		X	X		X
Height	X		-							
Weight / Waist Circumference/BMI	X		X		X		X	X		X
Complete Physical Examination	X		-							
Limited Physical Examination	-		X		X		X	X		X
Complete blood count with differential, , comprehensive metabolic panel, phosphorous, high sensitivity C-reactive protein			X		X		X	X		X
Total cholesterol, triglycerides, high density lipoprotein cholesterol, low density lipoprotein cholesterol, fasting glucose level, insulin, hemoglobin A1C, glucose tolerance test (GTT; optional), Plasma catecholamines fractionated (epinephrine,			X							X

norepinephrine, dopamine)										
Monocyte Assessment (Doublet %, Classical, Intermediate, Non-Classical circulating %, Total PBMCs , Viability, Monocyte Number/ml blood and , Monocyte gene expression)	X		X		X		X	X		X
Dispense monitoring device for electrodermal activity (Empatica E4 wristband) ± laptop (Optional)		X			X			X		
Return Empatica E4 wristband ± laptop (Optional)			X			X			X	
Psoriasis Flare or Rebound Assessment	-		X		X		X	X		X
Adverse Events	X	X	X		X		X	X		X
Clinical Efficacy Assessments										
PASI, BSA, sPGA	X		X		X		X	X		X
Pruritus VAS	-		X		X		X	X		X
Skin Discomfort/ Pain VAS	-		X		X		X	X		X
Subject Assessment of Joint pain VAS; Subject Global PsA VAS; HAQ-DI ⁿ	-		X		X		X	X		X
Subject Global Assessment of Psoriasis Disease Activity VAS	-		X		X		X	X		X
Health-related Quality of Life Assessments										
DLQI,	-		X		X		X	X		X
WPAI,	-		X		X		X	X		X
Stress Response Assessment										
Numerical N-Back			X	X						X
Investigational Product Dosing										
Dispense IP titration cards	-		X							
Dispense IP bottles	-		-		X		X	X		
Return IP tablets, Count for Compliance	-		-		X		X	X		X
Dispense Medication Log			X		X		X	X		
Return Medication Log					X		X	X		X

*Except for screening, all visits have a +/- 3 day window in which they can be completed.

**Diabetic patients will not undergo the glucose tolerance test for patient safety.

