Table of events. Body mass index (BMI) will be calculated.

- **Complete/Limited Physical Examination**

A complete physical examination includes evaluations of skin, nasal cavities, eyes, ears, lymph nodes, and respiratory, cardiovascular, gastrointestinal, neurological, and musculoskeletal systems. The complete physical examination is done at Screening and other designated visits. A limited physical examination includes evaluations of skin, lymph nodes, and respiratory, cardiovascular, and musculoskeletal systems. The limited physical examination is done at Baseline and other designated visits as indicated in Table of events.

- **Clinical Laboratory Evaluations**

Clinical laboratory evaluations will be performed as indicated in Table of Events. Clinical laboratory evaluations will include a complete blood count with differential (WBC, nucleated RBC, RBC, HGB, HCT, MCV, MCHC, PLT, RDW-CV, WBC differential, WBC absolute cell counts), a comprehensive metabolic panel (glucose, sodium, potassium, chloride, bicarbonate, anion gap, urea nitrogen, creatinine, GFR, calcium, albumin, alkaline phosphatase, total protein, AST, ALT, bilirubin total), phosphorus, and high sensitivity C-reactive protein. Total cholesterol, triglycerides, high density lipoprotein cholesterol (HDL-C), low density lipoprotein cholesterol (LDL-C), fasting glucose level, insulin, hemoglobin A1C, glucose tolerance testing (GTT; optional), and plasma catecholamines fractionated (epinephrine, norepinephrine, and dopamine) measurements are only required at baseline and week 16 as indicated in the table of events. Those subjects determined to have elevated lipids may elect to participate in a separate assessment characterizing their HDL. Monocyte labs will also be collected at each visit (Doublet %, Circulating Monocyte % (Classical, Intermediate, Non-Classical), Total PBMCs, Viability, Monocyte Number/ml blood). Patients with diabetes mellitus type I and type II will not undergo the GTT in order to maintain patient safety.

- **Monitoring Epidermal Activity (Optional)**

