6.2. Inclusion Criteria

Subjects must satisfy the following criteria to be enrolled in the study:

1. Males or females, ≥ 18 and ≤ 65 years of age at the time of signing the informed consent document.
2. Understand and voluntarily sign an informed consent document prior to any study related assessments/procedures being conducted.
3. Able to adhere to the study visit schedule and other protocol requirements.
4. Patients must exhibit AM-endotype psoriasis patients, identified by elevated ($>150\%$ of normal) levels of any one of the following criteria:
 - Intermediate (CD14⁺⁺CD16⁺) monocytes, OR
 - Circulating monocyte doublets, OR
 - Circulating monocyte-platelet aggregates (MPA).
5. Diagnosis of chronic plaque psoriasis for at least 12 months prior to Screening.
6. Have moderate to severe plaque psoriasis at Screening and Baseline as defined by
 - a. BSA $\geq 5\%$
 - b. sPGA ≥ 3 (moderate to severe)
7. Must be a candidate for phototherapy and systemic (including Otezla) therapy.
8. Must be in good health (except for psoriasis) as judged by the Investigator, based on medical history and physical examination.
9. Subject must have completed 5-7 days of successful Empatica device data collection. (Optional: Only if subject chooses to participate)
10. Subject must have consistent internet access and the ability to successfully download the Empatica data manager user interface. (Optional: Only if subject chooses to participate)

11. Females of childbearing potential (FCBP) must have a negative pregnancy test at Screening and Baseline. While on investigational product and for at least 28 days after taking the last dose of investigational product, FCBP who engage in activity in which conception is possible must use one of the approved contraceptive options described below:

Option 1: Any one of the following highly effective methods: hormonal contraception (oral, injection, implant, transdermal patch, vaginal ring); intrauterine device (IUD); tubal ligation; or partner's vasectomy;

OR

Option 2: Male or female condom (latex condom or non-latex condom NOT made out of natural [animal] membrane [for example, polyurethane]); PLUS one additional barrier method: (a) diaphragm with spermicide; (b) cervical cap with spermicide; or (c) contraceptive sponge with spermicide.

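### Does Section 9.1's silence on which pre-dose draw fixes the target marker build regression to the mean into the primary test?

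*Combined protocol and SAP*

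**What the plan says.** Section 9.1 defines the primary endpoint through a patient-specific marker: "For each subject, we will identify a target biomarker of abnormally elevated monocytes, among intermediate, doublets, and platelet doubles". If several are elevated, doublets come first, then intermediate monocytes. Every subject is said to end up with one marker. Its relative percent reduction from baseline to Week 16 is computed for each treated subject and tested against 0 with Wilcoxon's signed rank test. Neither the selection sentence nor the priority rule names a visit.

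The Table of Events (Section 4) marks the row "Monocyte Assessment (Doublet %, Classical, Intermediate, Non-Classical circulating" at Visit 1a and again at Visit 2A (Week 0), then at Weeks 4, 8, 12 and 16. Section 5 says the same in words: "Monocyte labs will also be collected at each visit (Doublet %, Circulating Monocyte % (Classical, Intermediate, Non-Classical), Total PBMCs". The Inclusion/Exclusion row is marked at 1a only. Under Length of Study, the protocol summary explains that Visit 1b exists to hand out a "device that cannot be given until their monocyte profile is known". Inclusion criterion 4 ("Patients must exhibit AM-endotype psoriasis patients, identified by elevated" levels of any one of three markers) gives no visit, whereas criterion 6, on skin severity, names both screening and baseline.

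**The concern.** A marker picked because it exceeds 150% of normal is, on average, partly high by chance. If that same value is also the starting point of the percent change, the chance part falls away by Week 16 with no drug effect. The primary test compares one treated group with 0, so the fall would be read as benefit, in the hypothesised direction. The ten healthy controls cannot reveal it: they are not selected for high values and do not enter the test.

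With two pre-dose draws and no visit named, an analyst could apply the priority rule to the 2A values. Some of the wording seems to lean that way. Section 2 makes baseline the starting point of all comparisons. The longitudinal paragraph says "we will longitudinally model these percent change values across time points (baseline, 4, 8, 12, and 16 weeks" and omits screening. The summary says patients "will be followed during treatment over 16 weeks with 5 monthly individual blood draws". Section 9.1 also has no rule for a marker that is elevated at 1a but not at 2A.

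**Working it through.** **1. Which draw the documents imply.**
- Eligibility is marked at 1a only, and the AM-endotype is an eligibility criterion.
- The profile is not known at 1a itself but is known before 1b, and 1a is the only monocyte draw before 1b.
- Titration cards are dispensed at 2A, so treatment starts on an endotype already established.
- Criterion 6 is re-checked at baseline and criterion 4 is not said to be. A patient with nothing elevated at 2A therefore stays in.
- Section 9.1 gives every subject one elevated marker and computes a reduction for every treated subject. Criterion 4 guarantees this on the entry draw. No rule guarantees it at 2A.

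**2. The plan's own power figure.** The planned reduction is 20%, "as long as standard deviation of percent change is not larger than 33" percent, so the effect size is 20/33 = 0.606. With N = 25 (Section 6.1), two-sided alpha 0.05 and effect size 0.60, simulating the exact signed rank test gives power 0.801. A noncentral t with n multiplied by 3/pi also gives 0.801. The stated 0.80 reproduces and does not depend on the choice of draw.

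**3. Noise level (assumed).** The documents give no repeatability. With within-patient log SD s and a uniform 20% reduction, the SD of percent change is 0.8 x exp(s^2) x sqrt(exp(2s^2) - 1).
- s = 0.15: 0.8 x 1.0228 x 0.2145 = 17.6%
- s = 0.25: 0.8 x 1.0645 x 0.3649 = 31.1%
- 33% is reached at s = 0.263, so 0.25 is close to the plan's limit even if drug response does not vary at all.

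**4. Simulation with no drug effect.** There were 10,000 trials of 25 patients per cell. Markers were centred at 1.0 or 1.3 times normal, with between-patient log SD 0.4 or 0.6, s = 0.15 or 0.25, and between-marker correlation 0 or 0.5. The 1a and 2A fluctuations were correlated 0 or 0.4. Entry required any marker above 1.5 times normal at 1a. Change ran from 2A to Week 16. The re-choosing rule kept the 1a marker when nothing was elevated at 2A; that fallback is invented, because the plan has none. False reductions are significant reductions, nominally 2.5%.

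| Markers, 1a-2A correlation | Re-chosen at 2A: median; false reductions | Fixed at 1a: median; false reductions |
|---|---|---|
| Three, 0 | 1.5-7.6%; 3.2-10.1% | about 0%; 1.0-1.6% |
| Three, 0.4 | 2.4-11.7%; 5.2-25.4% | 1.4-7.9%; 3.1-10.8% |
| Two, 0 | 0.8-4.9%; 2.2-5.2% | about 0%; 0.9-1.7% |

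The two-marker row uses doublets and intermediate monocytes only, because Sections 4 and 5 do not list platelet aggregates among the monocyte measurements. In the first row, the target differs between the two rules in 9-27% of patients, and the fallback is needed in 6-30%. At s = 0.15 alone, re-choosing gives a median of 1.5-2.9% and false reductions of 3.2-6.8%.

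**5. Wider assumptions.** Here total log SD was 0.4 or 0.6 and reliability 0.5 to 0.9, with independent errors and independent markers. Fixing at 1a again gives a median of 0%, with 0.7-1.8% false reductions. Re-choosing with the fallback gives 1.3-16.1% and 3.5-15.5%. The 16.1% comes from a cell where the SD of percent change under the 1a rule is 79%, or 0.8 x 79 = 63% at a uniform 20% reduction, far above the plan's 33%. Re-choosing and dropping patients no longer elevated at 2A gives 3.2-28.4% and 7.4-83.6%.

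**The case for a change.** The strongest opposing case is that the schedule settles eligibility, not the analysis target. No sentence carries the 1a marker into the analysis or forbids choosing again at 2A. In a single-arm test against 0 nothing would expose the artefact, and a sentence in 9.1 would cost almost nothing. The silence is real, and the direction of the bias under re-choosing follows whenever a marker fluctuates within a patient.

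The rest is weaker. The list of time points without screening belongs to the exploratory longitudinal model, and the count of five draws concerns the treatment period; neither says which draw selects. Re-choosing at 2A leaves some patients with no elevated marker, which conflicts with one marker for every subject. The most damaging variant, dropping those patients, conflicts with computing a reduction for each treated subject. The missing rule for a marker that has normalised by 2A is a gap only on the 2A reading; on the 1a reading the target carries forward.

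Two limits of the 1a reading should be admitted. If fluctuations persist between the visits, fixing at 1a still leaves a spurious median of 1.4-7.9% at correlation 0.4, more than half of the 2.4-11.7% under re-choosing. That comes from enrolling on high values in an uncontrolled pilot, and naming a draw would not remove it. Also, with three markers and independent fluctuations, about 13-46% of 1a targets would be at or below 150% of normal at 2A, so part of the primary analysis follows values no longer elevated. That is a fair price for separating selection from measurement.

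**Conclusion.** No change follows. This is an unwritten definition that an analyst can fill from the rest of the protocol: target from the Visit 1a entry draw, change from Visit 2A to Week 16. On that reading the median bias is about 0% if the 1a and 2A fluctuations are independent, and false reductions stay below the nominal 2.5%. The harmful alternative requires setting aside the endotype established at entry and inventing a rule the plan lacks. Even then, within the plan's own limit on spread and with independent fluctuations, the artefact is a median of 1.5-7.6% against a planned 20%.

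The textual reading is firm for entry and a reasonable inference for the analysis target. All bias sizes rest on assumed marker distributions and repeatability. The regression that remains if fluctuations persist is a caution for interpreting a single-arm pilot, and it is the same whether or not 9.1 names the draw. Whether platelet aggregates are measured at both pre-dose visits is a separate question about the schedule.

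### The exploratory longitudinal model treats baseline percent change, which is zero for every subject, as a response, so its time and Week 16 v baseline tests may not hold their nominal error rate (minor)

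*Combined protocol and SAP*

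**What the plan says.** Section 9.1 of the combined protocol and SAP gives each subject one target marker ("we will identify a target biomarker of abnormally elevated monocytes") and computes its relative percent reduction from baseline to Week 16. For the primary analysis, Wilcoxon's "signed rank test will be used to evaluate the null hypothesis of the median percent change being 0".

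The power statement in the same section is conditional: "power is 0.80 if the effect size is 0.60 or greater (assuming an underlying normal distribution"). It links this to a 20% median reduction: "as long as standard deviation of percent change is not larger than 33%, we will have effect size of at least 0.60".

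As a secondary, explicitly exploratory step, "we will longitudinally model these percent change values across time points (baseline, 4, 8, 12, and 16 weeks"), with time taken both as continuous and as categorical. The plan adds: "We will test for time effects, and consider post-hoc pairwise analyses of time points". It names no subject effect, covariance structure, transformation or symmetry check.

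**The concern.** Percent change from baseline, evaluated at baseline, is not a measurement. It is 0 for all subjects, with no spread. Entered as one of five responses in a model with a common residual variance, it does two things:

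- It distorts the pooled variance, because one visit contributes none of its own.
- It sets a fixed zero against post-baseline means. If percent change is skewed, those means differ from zero even when the median biomarker has not moved.

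Skew is possible because percent reduction is capped at +100% and has no lower limit. In the plan's own example, 1.5% to 1.2% is a 20% reduction; the reverse move is a 25% increase.

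At stake is the description of the trajectory: the time test and any pairwise comparison with baseline could report change too often or too rarely.

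**Working it through.** **Inputs.** From the plan: 25 completers (section 6.1); five time points, a 20% median reduction and an SD ceiling of 33% (section 9.1). Assumed, because the plan gives neither a shape nor a model: a log-normal biomarker, independent between visits given the subject, with per-visit log SD σ of 0.217 or 0.263; no true change; and an analysis with a subject effect, categorical visits and one residual variance.

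**1. The plan's own figure.** 20/33 = 0.606. Simulating the exact two-sided signed-rank test at n = 25 under normality gives power 0.801 at effect size 0.60 and 0.808 at 0.606. The stated 0.80 is right.

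**2. Scale of the assumed noise.** The log-ratio SD is s = σ√2: 0.217 gives 0.307 and 0.263 gives 0.372. With no change, the SD of percent change is √[exp(s²)(exp(s²) − 1)], which is 33% and 41%. The second level is above the ceiling under no change, but equals it at a 20% median reduction (0.8 × 41% = 33%).

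**3. The variance problem, for any symmetric shape.** Let percent change have SD S at each post-baseline visit, correlation ρ between those visits, and 0 at baseline. After removal of subject and visit effects, the expected residual variance is [4S² − (4S² + 12ρS²)/5]/4 = S²(0.8 − 0.6ρ). The model therefore gives Week 16 minus baseline the variance 2S²(0.8 − 0.6ρ)/25, while the true variance is S²/25. The ratio is k = 1.6 − 1.2ρ, and the error is about 2Φ(−1.96√k).

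| ρ | k | formula | simulated |
|---|---|---|---|
| 0.3 | 1.24 | 2.9% | 2.9% |
| 0.5 | 1.00 | 5.0% | 5.0% |
| 0.7 | 0.76 | 8.8% | 8.7% |
| 0.85 | 0.58 | 13.6% | 13.5% |

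The simulated overall time test gives 5.4%, 5.1%, 5.6% and 7.8%.

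**4. The mean problem, under the log-normal shape.** Here ρ = 1/(1 + exp(σ²)), about 0.49 at σ = 0.217, so k is close to 1 and the variance is nearly right. The trouble is the mean. With a median ratio of 1, the mean percent change is an increase of exp(s²/2) − 1, which is 4.8% or 7.2%. Against standard errors of 33/√25 = 6.6 and 41/√25 = 8.2 points, that is 0.73 and 0.88 standard errors from the fixed zero. Simulated error rates:

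| per-visit log SD | time, percent change | Week 16 v baseline, percent change | log values, time / Week 16 |
|---|---|---|---|
| 0.217 | 7.8% | 9.4% (0.4% reduction, 9.0% increase) | 5.0% / 5.1% |
| 0.263 | 8.9% | 11.2% | 5.0% / 4.9% |

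Leaving baseline out brings the time error on percent change to 4.8%, which locates the cause.

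**5. Dependence on the model.** With independent errors and no subject effect (σ = 0.217), percent change gives 1.2% for time and 3.3% for Week 16 v baseline. Log values without a subject effect give near 0%, because between-subject spread enters the error term. If subjects drift differently (log SD 0.2), a common-variance model gives 14.8% for Week 16 v baseline on percent change and 7.7% on log values; a paired contrast on log values gives 5.1%.

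**6. The primary test under the same shape.** With median ratio 0.8, the SD of percent change is 0.8√[exp(s²)(exp(s²) − 1)]. Power on percent change is 0.80 at SD 28% (s = 0.324) and 0.65 at SD 33% (s = 0.372); on the log ratio it is 0.90 and 0.80.

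**The case against.** The strongest reply is that the analysis is labelled exploratory, pairwise comparisons are only to be considered, and no model is named, so no particular error rate can be charged to the plan. That stands, and it is why the point is minor. The baseline zeros, however, do not depend on an assumed shape: they follow from the definition of percent change and the listed time points. A covariance that allowed baseline its own zero variance, or pairwise tests done as one-sample tests, would avoid most of the problem, but the plan does not say so.

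A reader might go further and infer that the primary test is on the wrong scale, or that its power is overstated. The documents do not support that. The 0.80 is tied to normality and reproduces. The log-normal shape is an assumption, and 33% is a ceiling, not an expected value. If 20% were the mean rather than the median reduction, power at SD 33% would be 0.86; with left-skewed ratios it would be 0.81-0.92.

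Percent reduction is also the plan's chosen and readily interpreted measure, and a log-scale primary test has costs of its own. If percent change is symmetric with SD 33%, false reduction under no change rises from 2.4% to 4.9%. If the baseline sample itself picks the target marker, the log scale worsens false reduction from regression to the mean: 14-44% against 8-32% at per-visit log SD 0.217, in an assumed selection model. Changing the primary scale is a trade-off, not a correction.

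**Conclusion.** The point holds for the exploratory longitudinal model and is minor. Treating baseline percent change as a response in a common-variance model gives wrong error rates: about 8-9% (time) and 9-11% (Week 16 v baseline) under the log-normal assumption with a subject effect; about 3-14% for Week 16 v baseline if percent change is symmetric and the correlation between visits runs from 0.3 to 0.85; and below 5% with independent errors. Size and direction rest on a model that the plan leaves open. The slope analysis with continuous time was not calculated.

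A reader might infer a risk of false efficacy. The figures do not show a lean that way. Under the log-normal shape the excess is almost all false increase. Under symmetry the error splits evenly, so neither direction is favoured, although at the highest correlation false reductions also rise (half of 13.5%, about 6.8%). In the primary test under no change, false reduction on percent change is about 1%. The primary analysis and its power statement stand.

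**What to change.** Choose one of two forms for the exploratory model and write it into section 9.1:

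1. Fit log biomarker values at all five visits, with a subject effect and unstructured covariance, or with paired contrasts for pairwise visits, and back-transform to percent reduction. The covariance must be stated, since the log scale alone does not cure a wrong one (7.7% against 5.1% in step 5).
2. Keep percent change, model Weeks 4-16 only, and compare each visit with baseline by a one-sample test against zero. This removes the variance problem but not the skew. With the signed-rank test, error under the log-normal shape is about 6.0% (1.2% + 4.75%) at per-visit log SD 0.217 and 6.4% (1.1% + 5.35%) at 0.263.

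Keep the primary signed-rank test on percent change. Add the signed-rank test on log(Week 16/baseline) as a prespecified sensitivity analysis, with a rule for zero readings. Limit it to the biomarker, because section 9.1 also says "Other outcomes such as PASI will be analyzed similarly" and the log rule should not carry over to PASI. A note to the power paragraph may say that under a log-normal ratio with a 20% median reduction, power on percent change is 0.80 at SD 28% and 0.65 at the 33% ceiling.

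The cost is a few SAP sentences and a little more analysis. No new visits are needed, since section 5 states: "Monocyte labs will also be collected at each visit". Two drawbacks should be recorded. The back-transformed estimate in form 1 is a geometric-mean ratio, not a median of percent changes. An unstructured covariance over five visits has 5 × 6/2 = 15 parameters, which is heavy for 25 subjects; paired contrasts are the simpler choice for pairwise visits.
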